1.2.4.2 Clinical pharmacokinetics

Ketamine is a racemic mixture consisting of (S)- and (R)-ketamine. As an anaesthetic for humans, (S)-ketamine is reported to be twice as potent as the racemic mixture and approximately three times more potent than (R)-ketamine. The pure S-ketamine stereoisomer is also marketed (e.g. Ketanest). In this trial, the racemic form will be used as it appears to cause more pronounced cognitive impairment at equianalgesic doses of the stereo-isomeric [R19-1359].

Ketamine is administered to humans via multiple routes, including i.v., i.m., oral, intranasal, epidural and intrarectal. However, the most common route of administration is via i.v. infusion. Following i.v. administration, the ketamine concentration has an initial alpha phase lasting about 45 minutes (half-life of 10 to 15 minutes) that corresponds clinically to the anaesthetic effect of the drug. The anaesthetic action is terminated by a combination of redistribution from the CNS to slower equilibrating peripheral tissues and by hepatic biotransformation to its less active metabolite norketamine. The later half-life of ketamine (beta phase) is 2.5 hours [R19-0414]. Oral administration is less preferable as due to its extensive first-pass hepatic metabolism the oral bioavailability of ketamine (16%–29%, with peak concentration levels of the drug occurring within 20–120 minutes) is limited [R19-0419]. Ketamine undergoes extensive metabolism starting with demethylation to norketamine primarily by CYP2B6 and CYP3A4. CYP3A4 demethylates the (S)-ketamine enantiomer more rapidly than the (R)-ketamine enantiomer, whereas CYP2B6 demethylates both enantiomers of ketamine with near equal efficiency. Norketamine is further metabolized to the hydroxynorketamines (HNKs) and dehydronorketamine (DHNK). In addition to this major metabolic pathway further minor pathways exist [R19-0419].

Following an i.v. sub-anaesthetic (antidepressant) dose of ketamine (0.5 mg/kg administered over a 40-minute infusion) plasma levels of ketamine were below detectable levels within 1 day; however, circulating levels of DHNK and HNK were observed for up to 3 days [R19-0419]. In adult humans, racemic ketamine has a high volume of distribution ($V_d = 3-5$ l/kg), a fast systemic clearance (26.3 ± 3.5 ml/kg) and a short elimination half-life (2–4 h). Compared to the racemic mixture, the elimination half-life of (S)-ketamine is slightly longer (5 h) and its systemic clearance is faster (14.8 ± 1.7 ml/kg). A possible explanation for this observation may be an inhibition of (S)-ketamine's clearance by the (R)-ketamine.

Elimination of ketamine is primarily via the kidneys, with low levels excreted as ketamine (2%), norketamine (2%), and DHNK (16%) whereas the majority of the drug (~80%) is excreted as hydroxyketamine (HK) and HNK.

1.2.4.3 Clinical safety

Ketamine is known to affect the cardiovascular and respiratory system. Commonly ($\geq 1/100$ to $< 1/10$) an increase in blood pressure, heart rate and respiratory rate is observed. However, although to a lesser rate (uncommon ($\geq 1/1,000$ to $< 1/100$)) an apparently opposite effect, namely bradycardia, arrhythmias and hypotension, as well as respiratory depression and laryngospasm and in rare cases ($\geq 1/10,000$ to $< 1/1,000$) obstructive airway disorders and apnoea can occur.

Proprietary confidential information © 2021 Boehringer Ingelheim International GmbH or one or more of its affiliated companies

Central nervous system and psychiatric disorders are also reported, ranging from common (hallucination, abnormal dreams, nightmare, confusion, agitation, abnormal behavior, nystagmus, hypertonia, tonic clonic movements), over uncommon (anxiety) to rare ones (delirium, flashback, dysphoria, insomnia, disorientation). If Ketamine is used as a general anaesthetic, an emergence delirium may occur (often consisting of dissociative or floating sensations) that some patients experience as unpleasant [R20-2543].

In addition, common adverse reactions are skin disorders (erythema, rash morbilliform), nausea and vomiting, and diplopia.

Anorexia, injection site pain and injection site rash are classified as uncommon and anaphylactic reactions, salivary hypersecretion, cystitis and haemorrhagic cystitis are rarely observed. After prolonged use (> 3 days or chronic use) abnormal liver function tests and Drug-induced liver injury has been reported, but the frequency cannot be estimated from the available data. In addition, single cases of increased intraocular pressure are known.

Ketamine has a wide safety margin; reported overdoses of Ketamine (up to 10 times that usually required) have been followed by prolonged but complete recovery [R20-2543].

For a more detailed description of ketamine profile, refer to the Ketamine hydrochloride (██████) Drug Label Information [R20-2543].

1.2.5 Residual Effect Period

The Residual Effect Period (REP) of ██████████, for lamotrigine 10 days, and for ketamine 24 hours. This is the period after the last dose with measurable drug levels and/or pharmacodynamic effects is still likely to be present.

1.3 RATIONALE FOR PERFORMING THE TRIAL

This exploratory trial is designed to investigate if there is a ██████████ effect of BI 409306 and BI 425809 in an ██████████. In this pharmacological model in healthy volunteers (as described in Section 1.2.3.1), infusion of the ██████████

[R13-0697], [P19-01512].

██████████ affects various ██████████ and ██████████
██████████ specific disruption ██████████

[R19-4239], [R19-4224]. In preclinical models, an effect on ██████████ was also seen. Moreover, effects of ██████████ on ██████████ was observed in human subjects [R20-0059], [R20-0060]. Similarly, ██████████ induces effects in ██████████ ██████████ [R19-3170], [R19-3171]. Pre-treatment with drugs that reduce or counteract the effects of ██████████ should therefore result in a measurable improvement in the mentioned ██████████ and thereby in the respective ██████████

Proprietary confidential information © 2021 Boehringer Ingelheim International GmbH or one or more of its affiliated companies

BI 409306 is a [REDACTED] in clinical development. As [REDACTED] its [REDACTED] should restore [REDACTED] due to [REDACTED] to physiological levels and give rise [REDACTED] manifestation of [REDACTED] [R10-5110], [P10-10289], [R10-5097].

BI 425809 is a [REDACTED] in clinical development that is targeting [REDACTED] with [REDACTED] Inhibition of [REDACTED] leads to [REDACTED] of [REDACTED] showing efficacy in [REDACTED] are available as well as indirect evidence of BI 425809's pharmacodynamic efficiency in humans ([REDACTED]). [REDACTED] treatment with BI 425809 resulted in improved [REDACTED] in patients with [REDACTED].

Considering the mode of action of BI 409306 and BI 425809 as well as ketamine, BI 409306 and BI 425809 are expected to [REDACTED].

Lamotrigine, a drug with a known positive effect on [REDACTED] [REDACTED] -0417].

1.4 BENEFIT - RISK ASSESSMENT

For details on the specific benefit/risk assessment of participation of healthy subjects in this clinical study in context of the COVID-19 pandemic, refer to Appendix [10.7](#).

Participation in this clinical trial is without any (therapeutic) benefit for healthy subjects. Their participation, however, is of major importance to investigate the effect of BI 409306 and BI 425809 on [REDACTED]. Subjects are exposed to risks of study procedures and risks related to the exposure to the trial medication and ketamine.

Procedure-related risks

The use of an indwelling venous catheter or venepuncture for e.g. blood sampling may result in mild bruising, and in rare cases, in transient inflammation of the wall of the vein, or nerve injury, potentially resulting in paraesthesia, reduced sensibility, and/or pain for an indefinite period.

The total volume of blood withdrawn per subject during the entire study will not exceed the volume of a normal blood donation (500 mL). No health-related risk to healthy subjects is expected from withdrawal of this volume of blood.

Drug-related risks and safety measures

Risks related to BI 409306 administration

Based on the results from completed trials in healthy volunteers, main adverse events are [REDACTED]

see Section 1.2.1).

(also refer to Section [1.2](#)).

Thus, for this trial the assumed therapeutic dose of [REDACTED] (single dose) was selected that was shown to be safe and well tolerated in healthy volunteers.

Risks related to BI 425809 administration

Based on the results from completed Phase I/II trials, the main dose-limiting AEs observed so far, were [REDACTED]

Risks related to lamotrigine administration

The selected dose of 300 mg of lamotrigine is a dose commonly used in the setting of such a ketamine challenge trial (Section 1.2.2) with no published safety concerns, including rash, so far. However, for patients treated with lamotrigine further serious adverse reactions, including serious rashes, have been reported, therefore specific safety measures will be implemented (see further below).

Risks related to ketamine administration

Ketamine is a broadly used drug and has a long history of clinical use. The dose administered in this trial is sub-anaesthetic and has been used safely as a challenge agent for cognitive effects before, alone as well as in combination with lamotrigine [R19-1361], [R19-1360], [R19-0417]. BI 409603 and ketamine, as well as BI 425809 and ketamine, have not been administered together so far. However, considering their modes of action, ketamine causing

Proprietary confidential information © 2021 Boehringer Ingelheim International GmbH or one or more of its affiliated companies

NMDA-receptor hypofunction and BI 409306 and BI 425809 attenuating NMDA receptor hypofunction you would rather expect an attenuation of ketamine induced psychotomimetic effects.

To minimize the risk for subjects the following safety measures will apply:

- Careful selection of eligible subjects (ref Section [3.3.2](#) and [3.3.3](#))
- Investigators will pay special attention to
 - The skin of subjects to detect any early sign of rash and check for lymphadenopathy (targeted physical examination as indicated in the [Flow Chart](#))
 - Any signs of mood change in the subjects
 - Any symptoms of pathologic immune activation, e.g. fever, lymphadenopathy. In this case, the subject should be evaluated immediately, considering a diagnosis of HLH or DRESS
 - Any signs of meningitis (e.g. stiff-back)
- Subjects will be instructed prior to lamotrigine treatment
 - To observe their own skin carefully and report any changes
 - That a rash or other signs or symptoms of hypersensitivity (e.g., fever, lymphadenopathy) may herald a serious medical event and that, the subject should report any such occurrence to a trial staff immediately.
- Any new rash will be evaluated by a licensed medical practitioner qualified to evaluate dermatological abnormalities. If the rash is then deemed of clinical significance or of indeterminate significance, the subject will be referred to a dermatologist
- In case a subject develops rash/signs of pathologic immune activation after drug administration he will not be dosed again (ref Section [3.3.4.1](#))
- Resuscitative equipment should be ready for use
- The subject will be informed before the first ketamine infusion that he may experience psychotomimetic symptoms and that he can request to stop the infusion at any time
- The initial intravenous ketamine bolus has to be administered over a period of 60 seconds as more rapid administration may result in respiratory depression or apnoea and enhanced pressor response
- Close monitoring of blood pressure, pulse rate and oxygen saturation during and after ketamine infusion

Proprietary confidential information © 2021 Boehringer Ingelheim International GmbH or one or more of its affiliated companies

- Continuous ECG monitoring during and after ketamine infusion until confirmation of recovery from ketamine
- Recovery from the ketamine administration will be followed up for at least 60 min after stop of infusion, until confirmation of recovery from ketamine as per criteria of recovery from ketamine, and must be documented. (see Section [5.2.5.6](#)).

- Visual acuity test will be performed at the Screening Examination and the End of Trial Examination, and also in case visual disturbances develop. Subjects with ophthalmologic disorders will be excluded from the study.
- Regular safety laboratory examinations, including haematology to monitor for blood dyscrasias
- Only healthy subjects with no co-medication will be enrolled.
- In case AEs occur that require treatment, anti-epileptic drugs (AEDs) are not allowed
- Prior to discharge the subjects will be assessed by an investigator for their fitness, including a DSST, MOAA/S, CADSS and a SFST, and suicidality including C-SSRS. Their in-house refinement can be extended anytime if deemed necessary by the medical judgment of the investigator
- Subjects will be informed that driving an automobile, operating hazardous machinery or engaging in hazardous activities should not be undertaken for 24 hours or more after ketamine infusion

Drug-induced liver disease

Although rare, a potential for drug-induced liver injury (DILI) is under constant surveillance by sponsors and regulators. Therefore, this trial requires timely detection, evaluation, and follow-up of laboratory alterations in selected liver laboratory parameters to ensure subjects' safety; see also Section [5.2.6.1.4](#), adverse events of special interest.

Summary

Considering the good safety profile of BI 409306 and BI 425809 observed so far, the published tolerability data of the ketamine challenge model with and without lamotrigine and the implemented safety measures, the overall potential risk for participating subjects is considered to be low. Successful investigation of a pro-cognitive effects of BI 409306 and 425809 would provide further evidence of their potential for clinical development.

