1.2.3.1 Clinical pharmacokinetics

After oral administration lamotrigine is rapidly and completely absorbed with negligible first-pass metabolism (absolute bioavailability is 98%, no food effect). Peak plasma concentrations occur within 1.4 to 4.8 hours following drug administration. Lamotrigine is marketed in different formulations, namely as a chewable/dispersible and as a compressed tablet. However, in terms of rate and extent of absorption the lamotrigine chewable/dispersible tablets were found to be equivalent, whether they were administered dispersed in water, chewed and swallowed, or swallowed as whole, and they were also equivalent to the lamotrigine compressed tablets [\[R19-0416\]](#). Lamotrigine exhibits linear kinetics in healthy volunteers over a dose range of 50 – 400 mg. In vitro data show that lamotrigine is not highly bound to plasma proteins (approx. 55% bound in human plasma). Clinically significant interactions with other drugs through competition for protein binding sites are unlikely. In accordance with this, no change in protein binding was observed for combinations of lamotrigine and phenytoin, phenobarbital, valproate or carbamazepine [\[R19-0416\]](#).

Lamotrigine is metabolized predominantly by glucuronic acid conjugation via Uridine 5'-diphospho-glucuronyl transferases (UGT). Its major metabolite is an inactive 2-N-glucuronide conjugate. Drugs that induce or inhibit glucuronidation may therefore affect the apparent clearance of lamotrigine. Strong or moderate inducers of the cytochrome P450 3A4 (CYP3A4) enzyme, which are also known to induce UGT may also enhance the metabolism of lamotrigine. For example, rifampicin, phenytoin, and phenobarbital reduce lamotrigine concentration by approx. 40% due to induction of lamotrigine glucuronidation. After oral administration of ¹⁴C-lamotrigine to healthy volunteers, 94% (10% unchanged) was recovered in the urine and 2% was recovered in the faeces.

In healthy volunteers, following single doses of lamotrigine from 50 to 400 mg, elimination half-life ($t_{1/2}$) averages 33 hours. The $t_{1/2}$ decreased by an average of 26% (mean steady state $t_{1/2}$ of 26.4 hours) following repeated dosing in healthy volunteers. In patients taking further anti-epileptic drugs (AED) half-life varied depending on concomitant AEDs. [\[R19-4225\]](#)

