4.2 OTHER TREATMENTS, EMERGENCY PROCEDURES, RESTRICTIONS

4.2.1 Other treatments and emergency procedures

No specific rescue medication is foreseen for BI 409306 and BI 425809, and there are no special emergency procedures to be followed. No additional treatment is planned. However,

Proprietary confidential information © 2021 Boehringer Ingelheim International GmbH or one or more of its affiliated companies

if adverse events require treatment, the investigator can authorise symptomatic therapy. In those cases, subjects will be treated as necessary and, if required, kept under supervision at the trial site or transferred to a hospital until all results of medical evaluations are acceptable.

In case of ketamine overdose, respiratory depression can occur requiring supportive ventilation. Each time after start of ketamine infusion until confirmation of recovery from ketamine, oxygen saturation (SaO₂) will be monitored continuously, and if SaO₂ is <90%, a prompt medical evaluation is to be done. Mechanical support of respiration that will maintain adequate blood oxygen saturation and carbon dioxide elimination is preferred to administration of analeptics.

- In case of clinically significant changes in blood pressure and pulse rate during the ketamine infusion, the infusion has to be stopped immediately. Treatment, e.g. with α₂-agonists (e.g. Clonidine) or β-blockers may be initiated in case of sustained and severe hypertension and tachycardia [[P19-11590](#)].
- If the subject experiences distressing psychomimetic symptoms, the ketamine infusion has to be stopped and further treatment with benzodiazepines, such as midazolam or diazepam may be indicated [[P19-11590](#)].
- If the subject experiences distressing psychomimetic symptoms, the ketamine infusion has to be stopped and further treatment with benzodiazepines, such as midazolam or diazepam may be indicated [[P19-11590](#)].
- In the rare event of ketamine-induced seizures, treatment should be started with benzodiazepines followed by barbiturates or propofol if persistent [[P19-11590](#)].

Following a suspected lamotrigine overdose, hospitalization and general supportive care is indicated, including frequent monitoring of vital signs and close observation of the patient. Induction of emesis should be considered. It is uncertain whether haemodialysis is an effective means of removing lamotrigine from the blood.

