4.2.2 Restrictions

4.2.2.1 Restrictions regarding concomitant treatment

In principle, no concomitant therapy is allowed. All concomitant or rescue therapies will be recorded (including time of intake on study days) on the appropriate pages of the CRF.

- Paracetamol and diclofenac must be avoided as symptomatic therapy of AEs due to its potential liver toxicity. Ibuprofen may be used if needed.
- Anti-epileptic drugs (AEDs) are not allowed due to their potential impact on the PK characteristics of lamotrigine.

Proprietary confidential information © 2021 Boehringer Ingelheim International GmbH or one or more of its affiliated companies

- Carbamazepine, extracts from Gingko, artemisinin, enzalutamide, efavirenz, lopinavir, ritonavir, tipranavir, rifampicin are not allowed due to CYP2C19 induction potential.
- Allicin, indomethacin, fluvoxamine, fluoxetine, ticlopidine, moclobemide, etravirine, ketoconazole (non-topical), voriconazole (non-topical), fluconazole (non-topical), esomeprazole, lansoprazole, pantoprazole, or omeprazole are not allowed due CYP2C19 inhibition potential.
- Ciprofloxacin, enoxacin, cinafloxacin, zafirlukast, oltipraz, mexiletine, phenylpropanolamine, methoxalen, hormonal oral contraceptives and hormonal replacement therapy are not allowed due to potential for CYP1A2 inhibition.
- The use of moderate and strong CYP3A4 inhibitors and inducers is not permitted.
- CYP3A4 sensitive drugs with narrow therapeutic range are not permitted during the trial period.
- Use of N-methyl-D-aspartate (NMDA)-antagonists (except ketamine administration as indicated in the [Flow Chart](#)) such as amantadine, or dextromethorphan

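### The unqualified ban on anti-epileptic drugs in Sections 1.4 and 4.2.2.1 is not reconciled with the seizure instruction in Section 4.2.1, and the protocol does not say which prevails

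*Protocol*

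**What the plan says.** Three protocol sections bear directly on this point, and a fourth gives background.

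- **Section 1.4**, in the list of measures meant to minimise risk to subjects: "In case AEs occur that require treatment, anti-epileptic drugs (AEDs) are not allowed". No reason and no exception are given.
- **Section 4.2.2.1**, on concomitant treatment, opens with "In principle, no concomitant therapy is allowed" and later states: "Anti-epileptic drugs (AEDs) are not allowed due to their potential impact on the PK characteristics of lamotrigine". Again there is no exception.
- **Section 4.2.1**, on other treatments and emergency procedures, gives a general permission ("if adverse events require treatment, the investigator can authorise symptomatic therapy") and a specific instruction: "In the rare event of ketamine-induced seizures, treatment should be started with benzodiazepines followed by barbiturates or propofol if persistent". It does not mention the ban.
- **Section 1.2.3.1**, on lamotrigine pharmacokinetics: "rifampicin, phenytoin, and phenobarbital reduce lamotrigine concentration by approx. 40% due to induction of lamotrigine glucuronidation".

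The SAP does not address the matter. It repeats the general statement on concomitant therapy and describes how such therapy will be coded and listed.

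**The concern.** A ketamine-induced seizure is an adverse event that requires treatment. Section 1.4 is worded for that situation and rules out a class of drugs. Section 4.2.1 names the event and calls for drugs that at least partly fall, or may be read to fall, in that class. Staff who look up one section find an instruction that the other does not support, and nothing in the protocol tells them which to follow.

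What is at stake is subject safety in a situation that leaves little time to resolve a conflict in the text. The subjects are healthy volunteers who, as Section 1.4 says, have no therapeutic benefit from taking part. Each completer receives four ketamine infusions, one at screening and three in the treatment periods. There is also a smaller compliance issue: read literally, following Section 4.2.1 could be recorded as a deviation from 1.4 and 4.2.2.1.

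**Working it through.** There is no figure to reproduce. The check sets the passages side by side.

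**Step 1. Do the rules cover the same event?** Section 1.4 applies when an adverse event needs treatment. Section 4.2.1 applies when ketamine causes a seizure. The second is a case of the first, so both apply. Section 4.2.2.1 is a general restriction on concomitant therapy, but it also says that rescue therapies are to be recorded, so rescue use is not plainly outside its scope.

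**Step 2. Do the drugs overlap?** The protocol does not list or define anti-epileptic drugs, so each class named in Section 4.2.1 has to be taken in turn.

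| Class in 4.2.1 | Place in the sequence | Link to the ban in the protocol's own text |
|---|---|---|
| Benzodiazepines | first | None stated. They overlap only if read as anti-epileptic drugs, for instance because they are given here to stop a seizure. |
| Barbiturates | second, if the seizure persists | Section 1.2.3.1 names one barbiturate, phenobarbital, among drugs that lower lamotrigine concentration by about 40%. That is the kind of effect Section 4.2.2.1 gives as the reason for the ban. |
| Propofol | second, as alternative to barbiturates | None stated. |

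The barbiturate step is therefore anchored in the documents. The benzodiazepine step depends on a class membership that the protocol never states.

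**Step 3. Does any text resolve the overlap?** Section 1.4 does not refer to 4.2.1. Section 4.2.2.1 neither refers to 4.2.1 nor exempts emergencies. Section 4.2.1 does not say that it overrides the other two. No precedence rule was found elsewhere in the supplied text.

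**Result.** Two unqualified bans stand against one specific emergency instruction. The overlap is clear for barbiturates and possible for benzodiazepines, and nothing decides between the texts.

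**The case against.** The best defence is that the specific rule governs the general one. Section 4.2.1 is the emergency section, it names this event, and it says that subjects will be treated as necessary. Section 4.2.2.1 opens with a qualifier; if it overrode 4.2.1, its general exclusion of concomitant therapy would also forbid the blood-pressure treatments that 4.2.1 mentions. This carries weight against 4.2.2.1. It does not dispose of Section 1.4, which is itself specific to treating adverse events.

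Second, because propofol is offered beside barbiturates, a reader who counts only barbiturates as anti-epileptic can follow 4.2.1 without breaching the ban. That is correct, but the protocol does not tell the reader to take that route.

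Third, the event is described as rare, a history of seizures is exclusionary (Section 3.3.3), and Section 8 foresees urgent safety measures. These points lower the likelihood of harm but do not reconcile the text.

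Some stronger readings are tempting and are not supported:

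- *Sites would withhold seizure treatment.* Nothing in the documents shows this; many clinicians would simply follow 4.2.1.
- *The ban has no rationale in most infusions.* With 36 × 4 = 144 planned infusions and lamotrigine given before 24, one might say that 120 of 144 (83%) fall outside the pharmacokinetic reason. But the trial is double-blind (Section 4.1.5), so investigators cannot limit a ban to lamotrigine periods, and an enzyme inducer given earlier could affect a later lamotrigine period. The 18 sequences at 2 subjects each place lamotrigine in periods 1, 2 and 3 for 8 subjects each. Infusions before lamotrigine in those subjects, counting screening, number 8×1 + 8×2 + 8×3 = 48. With the 24 on lamotrigine, 72 of 144 fall at or before a lamotrigine dose. Neither count measures harm.
- *The benzodiazepine text for distressing psychomimetic symptoms is a second contradiction.* That text ("further treatment with benzodiazepines, such as midazolam or diazepam may be indicated") is permissive and does not concern seizures, so it adds little.
- *Rescue use would go unrecorded.* Section 4.2.2.1 already requires recording.

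**Conclusion.** The point holds as an internal inconsistency in the protocol. Sections 1.4 and 4.2.2.1 ban a drug class without exception or definition, while Section 4.2.1 calls for drugs that overlap with it in a named emergency, and no text says which prevails.

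The conclusion rests on two readings: that a ketamine-induced seizure is an adverse event requiring treatment, which is hard to dispute, and that at least some barbiturates fall within the ban, which Section 1.2.3.1 supports through phenobarbital. Extending it to benzodiazepines needs the further assumption that they count as anti-epileptic drugs.

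The scope is narrow: one rare event, with no effect on sample size, power or the primary analysis. It still merits correction, because it bears on subject safety and the correction is small. No view is taken on which clinical instruction is right.

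**What to change.** Reconcile Sections 1.4, 4.2.1 and 4.2.2.1 so that they give one instruction. In 1.4 and 4.2.2.1, state whether the emergency treatments named in 4.2.1 fall under the ban. Do this for each drug class, so that the missing definition no longer matters, and add a cross-reference to 4.2.1. If the answer changes what 4.2.1 may direct, amend that section to match. The choice belongs to the sponsor's medical team.

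The cost is about one sentence in each of two sections, by amendment or clarification letter. Study procedures outside the reconciled instruction, the sample size and the SAP do not change.
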